### **Exploratory Objectives**

To understand whether RPS has an effect on Emergency Room (ER) visits without admission.

Among those who end up hospitalized, we will explore whether RPS has an effect on:

1. Oxygen requirement
2. Need for mechanical ventilation
3. Duration of ventilation
4. Length of hospital stay
5. Levels of inflammatory markers routinely ordered as part of clinical care (CRP, LDH, D-dimer, Ferritin, IL-6)
6. Rates of discharge

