**Multicenter: University of Michigan ([name])**

**INSTRUCTIONS**

This template is intended to help investigators prepare a protocol that includes all of the necessary information needed by the IRB to determine whether a study meets approval criteria. **Read the following instructions before proceeding:**

1. Use this protocol template for a PI initiated study that includes direct interactions with research subjects. Additional templates for other types of research protocols are available in the system Library.
2. If a section or question does not apply to your research study, type “Not Applicable” underneath.
3. Once completed, upload your protocol in the “Basic Information” screen in IRES IRB system.

**SECTION I: RESEARCH PLAN****Section 1. Statement of Purpose:** State the scientific aim(s) of the study, or the hypotheses to be tested.

The coronavirus disease-19 (COVID-19) pandemic has caused significant distress, and grief around the world. Given the rising numbers of infected individuals in the United States (US) and need for hospitalization in at least 14% of infected patients (1), there is substantial strain on the health care system. Identifying ways to ameliorate the progression and severity of this infection and preventing hospitalization is critical in preventing break in capacity and overwhelming the healthcare system.

Currently, it is believed that COVID-19 infected patients undergo two phases of illness; viral replication and the more fatal phase of inflammation. Preventing the inflammatory phase has the potential to decrease hospitalization, use of ventilation and mortality. Accordingly, we are proposing to identify the role of resistant potato starch (a natural dietary supplement) in preventing the progression to the inflammatory phase through its immunomodulatory effects on the gut microbiome.

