has also been postulated that butyrate decreases Angiotensin Converting Enzyme 2 (ACE2) receptor expression, which is the main entry mechanism for COVID-19 into epithelial lung cells (16-19). Our preliminary data shows that within one week of being on RPS therapy (~20 grams twice daily), participants' stool butyrate levels increases (14). As RPS is a commonly used nutritional supplement, often used in gluten free cooking and baking, it offers minimal risk to participants in this proposed work. Furthermore, we have encountered only minimal adverse events and no serious adverse events from its use in our preliminary data in allo HCT patients (HUM00112318 under IND 132208) (14). Hence, we propose to enroll 1500 COVID-19 positive patients, who are being monitored in the outpatient setting, to receive 2 tablespoons (~ 20 grams) of RPS twice daily for 14 days vs. placebo to test **our hypothesis that RPS will reduce rate of hospitalization in COVID-19 patients**. Our primary outcome of interest will be rate of hospitalization for COVID-19 related complications and our secondary outcomes will be TTCA and symptom severity score (2). If our hypothesis is proven, this simple, minimal risk intervention, will have the potential to reduce healthcare burden and improve patient outcomes.

[figure not shown]

**Figure 2.** Schematic of the effect of RPS on lung inflammation

complications and our secondary outcomes will be TTCA and symptom

[figure not shown]
severity score (2). If our hypothesis is proven, this simple, minimal risk intervention, will have the potential to reduce healthcare burden and improve patient outcomes.

**Figure 1.** Schematic of the effect of RPS on lowering IL-6

[figure not shown]

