We will analyze the efficacy of RPS in relation to the primary outcome of hospitalization. If there is a significant difference between the two arm with p-value of <0.01, we will not continue the study. For data quality and integrity, we will also analyze the efficacy of RPS in relation to the secondary outcomes of TTCA and symptom severity score to assess efficacy and ensure no increase in harm in the intervention arm.

**Section 14. Statistical Considerations:** Describe the statistical analyses that support the study design.

**Study design/Study outcomes measures:** We will conduct a double-blinded, randomized clinical trial comparing RPS (~20g twice daily for 14 days) with placebo (non-resistant starch) in 1500 adults (age  $\geq 18$  years old) with COVID-19 diagnosis (defined by a positive swab) who are being managed in the outpatient setting. The primary outcome is hospital admission due to COVID-19 related complications. The secondary outcomes are TTCA and symptom severity score. We also will investigate some exploratory outcomes such as ER visits without admission, and among those hospitalized, we will explore differences in oxygen requirement, need for mechanical ventilation, duration of ventilation, length of hospital stay, levels of inflammatory markers routinely ordered as part of clinical care (CRP, LDH, D-dimer, Ferritin, IL-6), and rates of discharge between the RPS and placebo arms.

**Sample size and accrual:** Assuming a 14% admission rate in the placebo group, we calculated that a sample size of 1362 (we will enroll 1500 to account for 10% loss to follow up) will be required to provide 80% power (with a two-sided alpha level of 0.04 to detect an absolute reduction in hospital admission rates of 5% or more in the RPS group. **The primary analysis will be based on the intention-to-treat principle, with all patients included in their assigned group.**

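### Outcomes after admission are compared only among hospitalized participants, a group the treatment is meant to change, so the comparison is not randomized and can mislead in either direction

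*Combined protocol and SAP*

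**What the plan says.** The Exploratory Objectives of the combined protocol and SAP introduce six outcomes with "Among those who end up hospitalized, we will explore whether RPS has an effect on". They are oxygen requirement, need for ventilation, its duration, length of stay, inflammatory markers ordered in routine care, and discharge. Section 14 (Statistical Considerations) keeps the restriction: "among those hospitalized, we will explore differences in oxygen requirement, need for mechanical ventilation, duration of ventilation, length of hospital stay", followed by the markers and discharge. The only exploratory outcome not limited in this way is emergency visits without admission.

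The Background states "our hypothesis that RPS will reduce rate of hospitalization in COVID-19 patients", and Section 14 powers the trial "to detect an absolute reduction in hospital admission rates of 5% or more in the RPS group". The Statement of Purpose expects the treatment to act further down the same path: "Preventing the inflammatory phase has the potential to decrease hospitalization, use of ventilation and mortality".

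Intention-to-treat with all patients is stated for the primary analysis only. The documents give no all-randomized version of the six outcomes, no adjustment for selection into hospital, and no caution about interpretation.

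**The concern.** Randomization makes the two arms comparable at baseline. It does not make the admitted patients in one arm comparable with the admitted patients in the other when treatment influences admission. If RPS keeps some patients out of hospital, those left in the RPS hospital group differ from their placebo counterparts because of the treatment itself. A difference in ventilation or stay between the two groups then mixes any effect on the course of illness with a change in who is being counted.

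The objective is worded as a question about whether RPS has an effect, and Section 14 sets a 0.05 level for all analyses, so the plan does not mark these comparisons as descriptive. At stake is how the severity results are read. In a trial that succeeds on its primary outcome, a higher ventilated share among RPS admissions could be taken for harm, or a lower one for a benefit after admission, when either may reflect selection.

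**Working it through.** **Inputs from the documents.** Section 14 gives "Assuming a 14% admission rate in the placebo group", a 5-point absolute reduction (hence 9% with RPS), a "two-sided alpha level of 0.04", 80% power, 1362 evaluable and 1500 enrolled to allow for 10% loss.

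**Assumptions.** Allocation is 1:1, since the ratio is not stated. The number ventilated is hypothetical, since the documents give no ventilation rate. All ventilated participants are among the admitted.

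**The plan's own figure.** For 14% against 9% at two-sided 0.04 and 80% power, the pooled normal formula gives 682 per arm, 1364 in total. The unpooled form gives 1358. The stated 1362 is reproduced, so the design rates are a sound basis for what follows.

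**Expected admissions.** 1500 × 0.90 / 2 = 675 per arm. Placebo: 0.14 × 675 = 94.5, about 95. RPS: 0.09 × 675 = 60.75, about 61. About 34 fewer participants, or 5/14 = 36%, enter the RPS side of the comparison.

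**Ratio among the admitted.** Let v be the number ventilated and a the number admitted in each arm, with equal arm sizes. Then

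(v_RPS / a_RPS) / (v_plc / a_plc) = (v_RPS / v_plc) × (a_plc / a_RPS).

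The first factor is the all-randomized ratio. The second, at the design rates, is 14/9 = 1.56. Which admissions are prevented determines the first factor.

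- **Only milder admissions prevented, ventilation unchanged.** With 20 ventilated per arm, 20/675 = 3.0% in both. Among the admitted, 20/95 = 21% against 20/61 = 33%. With 15 per arm, 15/95 = 16% against 15/61 = 25%. A true ratio of 1 is shown as 1.56.
- **Ventilation reduced by 20%.** 0.80 × 14/9 = 1.24, so a benefit is shown as an excess.
- **Ventilation and admissions reduced equally, by 36%.** 9/14 × 14/9 = 1.0, so the benefit is hidden.
- **Mainly severe admissions prevented.** Ventilation then falls by more than 36%, the true ratio is below 9/14 = 0.64, and the admitted-only ratio falls below 1. The remaining RPS admissions are a milder group, so their course in hospital looks better even if RPS does nothing after admission. As an answer about what happens in hospital, the bias favours RPS.
- **No effect on admission or ventilation.** Both factors are 1 and no bias is expected.

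**Length of stay, mild-only case.** Assume 12 days for severe and 4 for milder admissions, 20% of placebo admissions severe, and 681 per arm (1362 / 2). Admissions are 0.14 × 681 = 95.3 and 0.09 × 681 = 61.3, with 0.20 × 95.3 = 19.1 severe in each arm. Mean stay among the admitted is (19.1 × 12 + 76.3 × 4) / 95.3 = 5.6 days on placebo and (19.1 × 12 + 42.2 × 4) / 61.3 = 6.5 on RPS. Per randomized participant it is 534 / 681 = 0.78 against 398 / 681 = 0.58 days. The direction reverses.

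**How often it would mislead, mild-only case.** Simulations of 4000 trials per scenario used 681 per arm and a ventilated share of 20% to 30% of placebo admissions. With ventilation unchanged, the admitted-only share was higher on RPS in 93% to 98% of trials and nominally significant for harm (two-sided 0.05) in 36% to 57%. With a true 20% reduction the figures were 75% to 83% and 11% to 17%. With no effect on anything, about 2% were significant for harm, as expected by chance.

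**The case against.** The strongest reply is that these are labelled exploratory, carry no power calculation and feed no stopping rule. Section 14 names tests only for the primary and secondary outcomes, and the Protocol Deviations section calls exploratory follow-up optional. This stands as a limit on importance. It does not remove the problem, because the plan still asks a causal question of a group selected by the primary outcome.

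The illustration can also be challenged. The Statement of Purpose expects admission, ventilation and mortality to fall together, so a one-third drop in admissions with ventilation unchanged is not the effect the investigators foresee. That is fair: under an equal reduction the admitted-only ratio is 1.0. Nor are the two worked examples significant in themselves: an uncorrected chi-square gives p = 0.10 for 20/95 against 20/61 and p = 0.17 for 15/95 against 15/61. The ventilated counts are assumed.

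A reader might infer that these comparisons are the only planned look at severe disease. The documents do not support that. The primary outcome includes admission for hypoxic respiratory failure or pneumonia and counts a COVID-19 death before admission. Deaths, life-threatening events and hospitalizations are serious adverse events and are tabulated for the monitoring committee. What is missing is narrower: an all-randomized efficacy analysis of ventilation, oxygen and stay.

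Finally, stay, ventilator time and routine markers are observed only in hospital. For durations this is answered by scoring 0 for those never admitted. For markers the objection stands, and they can only be described.

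**Conclusion.** The point holds for the six admitted-only outcomes. As written, they are non-randomized comparisons conditioned on the outcome RPS is meant to reduce. At the design rates the admitted-only ventilation ratio is 1.56 times the all-randomized ratio. Whether this shows as apparent harm, a hidden benefit or an apparent benefit depends on which admissions are prevented, and the documents do not settle that.

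Two stronger readings should be resisted. One is that a wholly inert treatment would look harmful; with no effect on admission, no bias is expected. The other is that the plan is bound to be biased against RPS if RPS works; the 21% versus 33% result needs the prevented admissions to be the milder ones and ventilation to be unchanged.

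The size rests on 1:1 allocation, 675 evaluable per arm, the design rates and hypothetical ventilated counts. Exploratory follow-up runs four months against one month for the primary outcome, so the admitted set may be larger than 95 and 61. This is a worthwhile, inexpensive improvement to exploratory outcomes and does not affect the primary or secondary analyses.

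**What to change.** In Section 14 and the Exploratory Objectives, define four outcomes for all randomized participants, compared by assigned arm:

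- proportion ventilated;
- proportion needing oxygen in hospital;
- days in hospital;
- days on ventilator.

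Score no or 0 for those never admitted. Rank death worst, which also brings in deaths before admission that an admitted-only table leaves out. State one window: either the four-month record review set for exploratory objectives, or day 30 named explicitly. Restrict oxygen to hospital use, because the phone questionnaire has no oxygen item and home use would not be captured reliably.

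Keep the admitted-only figures, including inflammatory markers and discharge, as descriptive tables with no between-arm test, and add a sentence that the admitted groups are not randomized groups.

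The cost is mainly wording. The Time and Events table already schedules record review for every participant to day 120, although completeness needs attention if that follow-up is treated as optional. The downside is low event proportions and many zeros in the duration outcomes. A rank test can handle the zeros, but precision will be modest.

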### **SUBJECT ELIGIBILITY**

Subjects must meet all of the selection criteria to be enrolled to the study. Study treatment may not begin until a subject has been consented and meets the eligibility criteria.

Inclusion Criteria (please also refer to **Table 1**)

Participants >18 years of age with who are:

1. COVID-19 test positive status
2. Monitored in the outpatient setting

### **Exclusion Criteria**

1. Inflammatory bowel disease
2. History of gastric bypass
3. Active Clostridium difficile infection
4. Active participation in another COVID-19 intervention trial
5. Any physical or psychological condition that, in the opinion of the investigator, would pose unacceptable risk to the patient or raise concern that the patient would not comply with protocol procedures
6. Reported allergy to potato-based starch or corn-based starch
7. Difficulty swallowing in order to prevent any aspiration risk
8. Currently taking any IL-6 inhibitors such as Tocilizumab for any disease condition

### **SUBJECT SCREENING, ENROLMENT, AND RECRUITMENT**

This study will be conducted at multiple sites. Patients >18 years of age with COVID-19 positive status and who are being monitored in the outpatient setting will be approached by phone. IRB-approved informed consent must be obtained from patients prior to the initiation of treatment on this protocol. After informed consent is obtained and prior to the initiation of protocol therapy, all patients satisfying the inclusion/exclusion criteria must have eligibility confirmed by the PI or Co-I of the study team at each site. The patient will not be considered enrolled in the study until all information is confirmed by the PI or Co-I.

### **Screen Failures**

Participants who are consented to participate in the clinical trial, who do not meet one or more criteria required for participation in the trial during the screening procedures, are considered screen failures. Screen failures will not be re-screened.

### **Randomization**

We will use stratified (by site) permuted block randomization and will generate randomization lists to be sent to the investigational pharmacy for packaging of starch and delivery to the designated participants.

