**Section 2. Background:** Patients suffering from COVID-19 have been shown to have significant inflammation resembling cytokine release syndrome (CRS) (6). It is thought that this inflammatory phase persisting even after viral suppression is what leads to the more fatal phase of COVID-19.(7,8). One of the most commonly elevated markers in COVID-19 patients has been shown to be interleukin (IL)-6.(6,7). To this effect an IL-6 inhibitor known as Tocilizumab, usually used in the treatment of inflammatory conditions including CRS, has been used to help modulate and reduce this exaggerated inflammatory response in COVID-19 patients (9). Tocilizumab is mainly used and studied in hospitalized patients who are showing signs of increased inflammation, but more research on interventions to slow the onset of inflammation and decrease hospitalizations in COVID-19 patients is needed. **Towards this effort, we propose to study the effects of RPS on the rate of hospitalizations in COVID-19 patients who have not yet required hospitalization.** Decreasing hospitalization rates is vital in preventing the current burden on our healthcare system and will minimize exposure of healthcare workers to this highly infectious disease. The rationale for using RPS to mitigate COVID-19 hospitalizations is based on the ability of resistant starch to decrease IL-6 in humans (Figure 1).(10,11). Furthermore, others, as well as our group, have shown that resistant starch increases butyrate levels (12-14), which in turn has been shown to reduce IL-6 production and overall inflammation (15). Additionally butyrate has also been shown to specifically decrease lung inflammation in animal models by suppressing inflammatory cytokine production (Figure 2) (16-20). As butyrate is produced in higher amounts in the gastrointestinal tract, it can be absorbed into the bloodstream and has been shown to have significant amelioration of lower respiratory infections and inflammation in humans (21). It

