#### Section 4. Research Plan:

##### Study Design.

This is a multicenter phase III randomized, placebo controlled, double blinded, clinical trial enrolling 1500 COVID-19 positive patients who are being managed as outpatients to investigate the role of RPS in incident hospitalization after COVID-19 diagnosis as well as the secondary outcomes of TTTR and symptom severity score. Participants will be enrolled from multiple sites. Patients will be identified via Electronic Health Record (EHR) using a real time compiled list of COVID-19 positive patients at University of Michigan, and will similarly be identified via an EHR compiled list at other sites. Initial screening will be conducted via review of the EHR and will be followed up by a telephone call to obtain informed consent and to confirm inclusion and exclusion criteria (**Table 1**). If subjects agree to participate in the study via phone and meet the inclusion criteria, an informed consent document will be sent to patients electronically for subjects to sign digitally via SignNow. Upon receipt of subject's informed consent documentation with approval to participate in our study, pre-packaged Bob's Red Mill® RPS vs. pre-packaged placebo consisting of iso-caloric digestible Bob's Red Mill® corn starch (non-resistant starch) will be delivered to their home, with printed instructions (see

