**Figure 7. Trial Design**

**attached instructions**) on how to take the RPS or placebo for the duration of the trial. Patients will be asked to take 2 tablespoons (~20 grams) of RPS in water or juice or applesauce (any cool substance to make it palatable) twice daily for 14 days with the same instructions for the placebo arm. Patients will be called every 2 days while taking RPS to assess symptoms and adverse events via a pre-specified questionnaire (**see attached questionnaire**) for the first 14 days and then will be called weekly until 30 days after the last dose of treatment. Patients are then followed via EHR to complete the 4-months follow up from the time of diagnosis (ie. COVID test positive) (**Figure 7**). Of note, the placebo will be identical in appearance and packaging as the RPS. Both food ingredients, placebo and RPS, are isocaloric (approximately 140 calories per day from either food ingredient). The placebo has been safely used as a control in human clinical trials (NCT 02763033, NCT01939600, NCT01708694).

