### **Subject Recruitment and Retention**

Subjects will be identified via the use of an EHR compiled list of COVID-19 positive patients who are outpatients. We will use medical records to obtain phone numbers. We will contact patients via phone and before discussing any material pertaining to the study, we will first inform the patients that this call is regarding a research study and if they would like they can opt out, to ensure that the option of opting out is given to the patient as early as possible. If the patient agrees to hear information regarding the study, we will provide an oral presentation of the study. Additionally, we will also post flyers at testing centers to give participants information about the study and the option to opt out. After presenting the study to patients by phone, an informed consent document will be sent to the patient electronically for subjects to sign digitally. After informed consent is obtained, screening to ensure that participants meet the inclusion/ exclusion criteria will be performed via phone and EHR. All follow up will be via phone calls and EHR review. The above plan was put together in order to limit contact with COVID-19 positive patients as the alternative of approaching and following the patients in person will put the research staff and the community at large at risk as it will promote the spread of this highly infectious virus by bringing these patients to the health system.

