**Packaging and Delivery of potato starch (active) and corn starch (placebo) (600 grams and 500 grams respectively):**

As this is a double blinded randomized control trial, investigators and participants will not be made aware of participant allocation to intervention or placebo starch.

To ensure blinded study design, as well as safe packaging and shipment of starch the following steps will take place:

- Starch was delivered from Bob's Red Mill free of charge to:  
Yale Investigational Pharmacy ([name])
- Similarly, starch was delivered from Bob's Red Mill free of charge to Michigan site.
- Only the pharmacist will hold the labeling key and will repackage the starch. The manufacturer packaging will be removed and the starch will be emptied into a pre-labeled freezer ziploc bag. To ensure secure packaging of starch, each amount (either 600 or 500 grams depending on type of starch) will be double bagged for safety. Labeling will comply with labeling regulations.
- Starch packages will be repackaged and labeled at Yale's investigational drug services (IDS) who will be responsible for dispensing the starch, keeping drug accountability logs and compliance with any relevant state requirements. Research study team will package the starch at University of Michigan and the IDS at Michigan will dispense and ship the starch accordingly.
- A generated list of enrolled participants randomized to intervention or placebo by stratified permuted block randomization will be given to IDS who will ship starch based on patient allocation.

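### Co-infected household members can be randomized to opposite arms at one address, and the plan has no rule to prevent or record it; the likely cost is modest and the remedy cheap

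*Combined protocol and SAP*

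**What the plan says.** The Randomization section reads: "We will use stratified (by site) permuted block randomization and will generate randomization lists to be sent to the investigational pharmacy". The Blinding section and the packaging section repeat the method. Site is the only stratification factor, and the participant is the unit allocated.

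Recruitment (Subject Recruitment and Retention): "Subjects will be identified via the use of an EHR compiled list of COVID-19 positive patients who are outpatients". Section 2, Background, calls COVID-19 "this highly infectious disease".

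No eligibility, screening or recruitment text mentions household: not Table 1, the Subject Eligibility lists, the screening procedures, Section 5, or the recruitment procedures in Section III. The nearest exclusion is "Active participation in another COVID-19 intervention trial", which concerns the patient's own participation in a different trial. The investigator-discretion exclusion likewise concerns the patient's own condition.

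On the product, Study Design says that it "will be delivered to their home, with printed instructions". The packaging section removes the manufacturer's packaging and says "the starch will be emptied into a pre-labeled freezer ziploc bag", and that "each amount (either 600 or 500 grams depending on type of starch) will be double bagged for safety". The text beside Figure 7 says that "the placebo will be identical in appearance and packaging as the RPS". The product specifications describe the potato starch as a white powder and the corn starch as a fine white powder (Appendices C and D).

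The participant instruction sheet (Appendix B) says nothing about sharing or keeping bags apart. The phone questionnaire (Appendix A) asks, yes or no, whether the starch was taken as instructed, with a reason if not.

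**The concern.** People in one household tend to be infected at about the same time, so several can be on the recruitment list together. Individual allocation can then put both starches in one kitchen, spooned out by the participants themselves. Two things are at stake.

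- **Contrast.** If members share, mix or use each other's bag, part of the treatment difference disappears for those pairs. Intention-to-treat analysis keeps the comparison valid but cannot restore the lost contrast.
- **Blind.** A participant living alone has no second bag to compare. A discordant pair has two, differing by 100 g in content and possibly in fineness. Time to clinical recovery and the symptom score both rest on self-report, so they are the outcomes exposed. Hospitalization is much less so.

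**Working it through.** **Inputs from Section 14 (sample size):** 14% admissions on placebo, an absolute reduction of 5 points (so 9%), two-sided alpha 0.04, 80% power, 1362 evaluable, 1500 enrolled. 1:1 allocation is assumed, since the documents do not state the ratio.

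**The plan's own figure.** The pooled-variance two-proportion formula without continuity correction gives 682 per arm, 1364 in total, against the stated 1362. It reproduces. With 681 per arm:

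- mean rate 11.5%; SE under the null = √(2 × 0.115 × 0.885 / 681) = 0.01729
- SE under the alternative = √((0.14 × 0.86 + 0.09 × 0.91) / 681) = 0.01724
- power = Φ((0.05 − 2.054 × 0.01729) / 0.01724) = Φ(0.841) = 80.0%

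There is no reserve. The 1500 matches 1362 × 1.1 = 1498, whereas 10% loss needs 1362 / 0.9 = 1514.

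**Assumptions not in the documents.** Let h be the share of participants who are in co-enrolled pairs, d the share of those pairs that are discordant, and L the share of the contrast that discordant pairs lose. Then x = h × d × L, the arm rates become 14% − 2.5x and 9% + 2.5x (in points), and the difference is 5(1 − x).

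**Choice of d.** Two people in the same permuted block of size b are discordant with probability (b/2)/(b − 1): 2/3 for b = 4 and 3/5 for b = 6. In different blocks it is 1/2. Block size is not stated. Section III targets 500 participants at Yale and Section 1 allows six months for treatment and data collection, so that site would randomize about 500 / 182 ≈ 2.7 a day. With small blocks, members enrolled a few days apart will usually fall in different blocks, so d = 1/2 is used.

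**Results (681 per arm, alpha 0.04, d = 1/2):**

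| Loss of contrast L | h = 10%: difference, power | h = 20%: difference, power |
|---|---|---|
| 10% | 4.975 points, 79.6% | 4.95 points, 79.2% |
| 50% | 4.875 points, 77.9% | 4.75 points, 75.7% |
| 100% (worst case) | 4.75 points, 75.7% | 4.50 points, 70.9% |

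Worked case, h = 20% and L = 100%: x = 0.10 and the rates are 13.75% and 9.25%. Power = Φ((0.045 − 2.054 × 0.01729) / 0.01725) = Φ(0.55) = 70.9%.

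**The blind.** The claim of identical appearance and packaging sits beside two bag contents, 600 g and 500 g by type of starch, and two powder descriptions. These passages need reconciling. A pair could see that their bags differ. To infer the arm, they would also need to know which property belongs to which starch. No numerical size can be put on this.

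**The case against.** The case for leaving the plan alone has real force.

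- **The bags are labeled.** They are labeled in advance and sent to designated participants, which lowers accidental mix-up. Label content is not shown. Adherence is asked every two days during treatment, and the Protocol Deviations section records deviations in treatment administration, so a reported mix-up has somewhere to surface. This stands, but none of it prevents sharing or comparison, and a yes/no item can miss use of the wrong bag.
- **The size is assumed.** The documents do not give h or L, and the bias is towards no difference, so it cannot manufacture a benefit. This stands.
- **Exclusion has its own cost.** At h = 10–20%, one per household removes h/2 = 5–10% of candidates (75–150 of 1500). If they were not replaced, power would be 77.9–75.6%, about the loss from 50% contamination. This stands, so the 1500 target must be kept.

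Three stronger readings are tempting, and the documents do not support them.

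- A reader might apply 2/3 discordance to every pair with complete loss of contrast, giving 74–68% power at the same h. That holds only if every pair falls in one block of 4 and every discordant pair loses the whole contrast.
- A reader might infer that household clustering can never be examined. Home delivery requires addresses, so co-enrolment could be reconstructed, although no such analysis is planned and the mixing itself would remain unrecorded.
- A reader might infer that side-by-side comparison reveals the arm. It shows only that the bags differ.

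**Conclusion.** The gap is certain and its size is not. The plan allocates individuals within site, recruits from a population in which household members are likely to be positive together, and has no rule for co-enrolment. With 10–20% of participants in co-enrolled pairs and half of pairs discordant, the power loss is under 1 point if 10% of the contrast is lost and about 2–4 points if half is lost. Complete loss in every discordant pair costs about 4–9 points and is a worst case. All of this rests on an assumed co-enrolment share and 1:1 allocation. The weakening of the blind is plausible for the two self-reported secondary outcomes but unquantified. Individual allocation within households does not of itself call for a variance inflation; the harm lies in contamination and comparison. This is an inexpensive improvement worth making and does not threaten the trial's validity.

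**What to change.** At the screening call, ask whether another household member is already randomized, and check the answer against the shipping address before randomization. Then choose one of two routes:

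- **(a) Exclude later members.** Add to Table 1 and to the Exclusion Criteria list: *another member of the same household is already randomized in this study*. Keep the target at 1500. Cost: 5–10% of candidates under the illustrated share, so accrual takes about 5–11% longer (1/0.95 = 1.05 to 1/0.90 = 1.11), roughly 10–20 days on six months.
- **(b) Give later members the first member's arm.** Keep the allocation concealed in the pharmacy, and replace the unadjusted chi-square and t-tests in Section 14 with analyses using household-clustered standard errors. Cost: a design effect of about 1 + h × ρ. For an assumed household correlation ρ of 0.05–0.1 and h of 10–20%, this is 1.005–1.02. The effective size per arm falls from 681 to 678–668 and power by about 0.2–0.8 points. A guess about one member's arm would also apply to the other.

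Under either route, record co-enrolment in the data and add to the instruction sheet in Appendix B that bags must not be shared. The address check uses information already needed for shipping.
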